6.7.2 Safety/Tolerability

6.7.2.1 Adverse Events

Only treatment emergent adverse events (AEs) will be analysed. These are adverse events that occurred after taking study medication. In particular this means only the following events are considered as treatment emergent:

START BLOCK: Events starting at visit 2 or later

STOP BLOCK: Events starting at visit 1 or later

In case of missing start data, adverse events are considered as treatment emergent.

Frequencies of subjects experiencing at least one AE will be displayed by body system and preferred term according to MedDRA terminology. Detailed information collected for each AE will include: A description of the event, duration, whether the AE was serious, intensity, relationship to trial drug, action taken, and clinical outcome.

Summary tables will present the number of subjects observed with AEs and corresponding percentages. Additional subcategories will be based on seriousness of event, event intensity and relationship to trial treatment.

An overview table will be produced showing the number of patients with

- any AEs
- any SAEs
- any deaths
- any severe AEs
- any related AEs
- any related severe AEs
- any related serious AEs
- any fatal related AEs
- any AEs leading to premature study discontinuation

A subject listing of all AEs will be prepared.

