Trial design	
Stop HCQ block
 
Open label treatment      Double blind treatment      Open observation
 
> 3 month      3 months      3 months
 
Stable baseline for -30 to -10 days
 
HCQ individual dose
 
no major changes in respiratory status or medication
 
Randomized withdrawal
 
placebo
 
No medication

This is an exploratory Phase 2a, randomized, double-blind, placebo-controlled, parallel-group, multinational withdrawal study in subjects with chILD and treated with hydroxychloroquine.

This study includes:

- History of Open Treatment Period (total of at least 3 months of continuing HCQ treatment until randomization)
- Screening Period (Day -30 through Day -10)
- Treatment Period (Day 1 through Day 84)
- Open observation period (Day 85 through Day 168)

Trial population	In addition to the block specific inclusion criterion the inclusion criteria are: See 3.6.1 in the protocol Allowed previous medication: see 4.1.10
	exclusion criteria: See 3.6.2
Trial duration	Until 2024/2025
Number of subjects	It is planned to enrol at least 80 subjects
Number of sites	Up to 100 trial sites are planned to participate
Primary outcome	START HCQ block Relative change trial day 1 (i.e. Visit 2) through day 28 (i.e. Visit 3) and relative change day 28 to day 56 (i.e. Visit 4) active compared to change placebo STOP HCQ block Relative change day 1 (i.e. Visit 2) through day 84 (i.e. Visit 5): change active compound compared to change placebo Oxygenation (see Table 3.3-1)
Secondary outcome	See 3.4

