## STOP HCQ block

Table 1-2

Visit	Visit 1 + Screening	Visit 2	Email- /Phone- Visit	Visit 3	Email-/ Phone- Visit	Visit 4	Email-/ Phone- Visit	Visit 5	Email-/ Phone- Visit	Visit 6	Email- /Phone- Visit	Visit 7	Email- /Phone- Visit	Visit 8
Action	„Begin of baseline“	“End of baseline“ + Day 1 of withdrawal treatment	2 weeks of withdrawal, at home	4 weeks of withdrawal treatment	6 weeks of withdrawal, at home	8 weeks of withdrawal treatment	10 weeks of withdrawal, at home	“End of trial“ after 12 weeks of withdrawal treatment	2 weeks of open observation at home	Follow up after 4 weeks of open observation	6 weeks of withdrawal, at home	Follow up after 8 weeks of open observation	10 weeks of withdrawal, at home	Follow up after 12 weeks of open observation
Trial day	-30 to -10	1	14 (-7, +7)	28 (-7, +7)	42 (-7, +7)	56 (-7, +7)	70 (-7, +7)	84 (-7, +7)	98 (-7, +7)	112 (-7, +7)	126 (-7, +7)	140 (-7, +7)	154 (-7, +7)	168 (-7, +7)
Demographics (e.g. sex, age)	X													
Patient information, informed consent	X													
Previous (last 12 months) and concomitant diseases	X	X	X	X	X	X	X	X	X	X	X	X	X	X
Previous (last 3 months) and concomitant treatments	X	X	X	X	X	X	X	X	X	X	X	X	X	X
Inclusion/exclusion criteria	X	X 												
Pregnancy test k	X*			X		X		X						
Randomization a	X													
Trial medication supply to patient		X		X		X								
History (cardiotoxicity, hypoglycaemia)	X	X		X		X		X		X		X		X
Physical examination	X	X		X		X		X		X		X		X
Vital signs (BP, pulse, temp) b	X	X		X		X		X		X		X		X
ECG j	X*							X						X
Ophthalmologic review l	X*													X 
Lab c (GOT/GPT/Crea/Potassium/CK/gGT/LDH/BB/DIF F / HCQ drug level, blood glucose)	X*			X		X		X		X (only HCQ drug level)		X (only HCQ drug level)		X (only HCQ drug level)
pO 2 , pCO 2 (capillary)	X	X 		X 		X 		X 		X 		X 		X 
O 2 -sat e , in room air	X	X	X	X	X	X	X	X	X	X	X	X	X	X
Respiratory rate, in room air	X	X	X	X	X	X	X	X	X	X	X	X	X	X

CONFIDENTIAL

Visit	Visit 1 + Screening	Visit 2	Email- /Phone- Visit	Visit 3	Email-/ Phone- Visit	Visit 4	Email-/ Phone- Visit	Visit 5	Email-/ Phone- Visit	Visit 6	Email- /Phone- Visit	Visit 7	Email- /Phone- Visit	Visit 8
Retractions	X	X	X	X	X	X	X	X	X	X	X	X	X	X
Coughing	X	X	X	X	X	X	X	X	X	X	X	X	X	X
Oxygen demand c	X	X	X	X	X	X	X	X	X	X	X	X	X	X

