#### **STOP HCQ block**

- To evaluate the efficacy of chronic (> 3 months) HCQ treatment in chILD compared to placebo.
- To evaluate the safety of HCQ after > 3 months of treatment in chILD.
- To evaluate blood levels of HCQ before and after treatment in chILD.

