3.	
Diagnosis of chronic (<math>\geq 3</math> wks of duration) diffuse parenchymal lung disease (DPLD = chILD), defined in at least one of the following ways:
 
a) chILD genetically diagnosed
 
Surfactant dysfunction disorders including patients with mutations in SFTPC, SFTPB, ABCA3, TTF1 (Nkx2-1), further extremely rare entities with specific mutations, for example in TBX4, NPC2, NPC1, NPB, COPA, LRBA and other genes. In this case, also previously preterm (<math>\leq 37</math> weeks of gestation) babies or children and adults of all ages can be included into the study.
 
b) chILD histologically diagnosed
 

• Chronic pneumonitis of infancy (CPI)

• Desquamative interstitial pneumonia (DIP)

• Lipoid pneumonitis / Cholesterol pneumonia

• Nonspecific interstitial pneumonia (NSIP)

• PAP after the exclusion of mutations in GMCSF-Ra/b and GMCSF autoantibodies*

• Usual interstitial pneumonia (UIP)

• Follicular bronchitis/ bronchiolitis/ Lymphogenic interstitial pneumonia (LIP)

• Storage disease with primary pulmonary involvement (e.g. Nieman Pick)

• Hermansky Pudlak Syndrome

• Idiopathic pulmonary haemorrhage (haemosiderosis)*

• Other histology diagnosing chILD, in particular combination of the above pattern, but not exclusively

4.	Start block: no HCQ treatment in the last 12 weeks

	Stop block: stable HCQ treatment for at least the last 12 weeks
5.	Ability of subject or/and legal representatives to understand character and individual consequences of clinical trial.
6.	Signed and dated informed consent of the subject (if the subject has the ability) and the representatives (of underaged children) must be available before start of any specific trial procedures.

\*may be diagnosed in the absence of a lung biopsy by characteristic lung lavage cytology (PAS stain, Fe stain), CT pattern or autoantibodies (gliadin, endomysium; cANCA) and clinical course.

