4.2.1 Efficacy

The following variables will be investigated:

- Oxygen saturation (O2-sat, in room air) (only absolute, as relative already primary outcome) assessed at every visit (not web/tele feedback)
- Respiratory rate (RR, in room air) (relative and absolute) assessed at every visit and every web/tele feedback
- Retractions (yes/no) assessed at every visit and every web/tele feedback
- Coughing last 24 h (yes/no) assessed at every visit and every web/tele feedback
- Oxygen requirement assessed at every visit and every web/tele feedback
- pO2, pCO2 (capillary, in room air)
- Chest x-ray scoring for chILD assessed at screening and visit 3 (START HCQ Block) and visit 5 (STOP HCQ Block)
- Overall survival
- If > 5y old
 - FEV1 % predicted (recorded in L)
 - FVC % predicted (recorded in L)
 - reference values according to the GLI 2012 lung function regression equations
 - 6 minutes walking distance (meter)
 - O2-saturation before and after 6MWT
 - Borg scale
- If ventilated:
 - Duration (h) of mechanical ventilation
 - NO (%), ECMO yes/no, if yes VA/VV, double lumen vs. single lumen, Flow-rate.

4.2.2 *Safety/Tolerability*

Adverse events, clinical laboratory values (GOT, Creatinine, gGT, blood count, differential, LDH, BNP, steady state drug level), ECG, ophthalmologic review

Adverse events will be documented during the study at each visit (exemption: START HCQ between Visits 1 and 2. However, occurring AEs between those visits are not treatment emergent).

Laboratory data will be assessed at screening, visit 3 and visit 4 in the START HCQ Block and at screening, visit 3, 4 and visit 5 and EDTA additionally at visit 6 in the STOP HCQ Block.

Vital signs (respiratory rate, height, weight, BMI, heart rate, blood pressure (systolic and diastolic), temperature, hypoglycaemia (yes/no), appropriate observation of blood glucose levels (yes/no), cardiotoxicity (yes/no), appropriate ECG (yes/no)) will be assessed at screening, and every following visit (not web/tele feedback).

A physical examination will be done at the same visits.

Symptoms and clinical course of treatment will be documented at the same time points as the physical examination is performed and at telephone contact visit.

4.2.3 *Quality of Life (Peds QL)*

Not applicable.

4.2.4 *Health Economics*

Not applicable.

5 Treatment of Missing Values and Outliers

5.1 *Missing Values*

No substitution of missing values is planned.

5.2 *Outliers*

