There will be no methods employed for detecting outliers.

6 Statistical Analyses

The default summary statistics for quantitative variables will be the number of observations (n), mean, standard deviation (SD), median, first quartile (Q1), third quartile (Q3), minimum and maximum for those patients with data available.

For qualitative variables, the number (n) and percentage (%) of patients with non-missing data per category will be the default summary presentation. If appropriate, the number of missing values will be displayed as a “Missing” category.

A value will be considered missing if a patient attends the visit (visit date is available) but no value is documented.

All variables will be displayed by treatment group and with a total column.

Listings of all AE data available will be provided only.

6.1 *Patient Disposition*

The following patient disposition variables will be presented by numbers and percentages:

- Informed consent given to study participation / study treatment
- Inclusion and exclusion criteria

- Size of analysis populations (enrolled, ITT, safety)
- Study completion according to protocol
- Reasons for premature discontinuation of study treatment
- Type of major protocol violation

Protocol deviations which are documented in the CRF will be listed additionally.

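### The STOP adverse-event window opens before the first study dose, switched START patients have no table column, and the SAP contradicts itself on whether adverse-event tables will exist

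*SAP*

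**What the plan says.** **Treatment-emergent definition (SAP 6.7.2.1).** Only treatment-emergent AEs are analysed: "These are adverse events that occurred after taking study medication". The section then spells this out by block. START opens at Visit 2. STOP reads: "STOP BLOCK: Events starting at visit 1 or later". Neither window has a stated end, and AEs with missing start data count as treatment emergent.

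**The same interval in START (SAP 4.2.2).** On AEs between Visits 1 and 2: "However, occurring AEs between those visits are not treatment emergent". Nothing equivalent is said for STOP.

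**STOP timing (Protocol Synopsis and Table 1-2).** Visit 1 lies between Day -30 and Day -10. The row "Trial medication supply to patient" is first marked at Visit 2, which is Day 1. Blinded treatment runs to Day 84 (Visit 5, labelled as the end of trial). Open observation follows to Day 168, with AEs still scheduled.

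**What STOP patients take at Visit 1 (Protocol 3.6.1).** "Stop block: stable HCQ treatment for at least the last 12 weeks". A secondary objective in Protocol 2.2 is "To evaluate the safety of HCQ after > 3 months of treatment in chILD".

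**Columns.** SAP 6: "All variables will be displayed by treatment group and with a total column". SAP 2.1 places safety subjects by the treatment they in fact received. SAP 1.2 has the START placebo group switch to active drug.

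**Outputs.** SAP 6 says AE data will be provided as listings only. SAP 6.7.2.1 plans frequency tables by body system and preferred term, summary tables and an overview table. Protocol 8.4 also plans tables.

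**Compliance (SAP 6.5).** Capsules used are divided by the days from randomisation to study end. Study end is not defined. SAP schedule footnote a requires randomisation at least 1 week before the first dose.

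**The concern.** The STOP rule does not follow from the definition it is meant to spell out. Between Visits 1 and 2 no STOP patient has taken study medication. All of them are on their own HCQ, including those who will receive placebo. In a table by treatment group, those patients' run-in events would be shown under placebo although they arose on HCQ.

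In START, a patient who takes placebo for 28 days and then HCQ for 28 days has received both treatments. The assignment rule does not say which column takes that patient, or whether the events should be split. The only placebo-controlled part of START, Day 1 to Day 28, is therefore not shown on its own.

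Safety is a stated secondary objective in both blocks (at 28 and 56 days in START, after more than 3 months in STOP). These tables, if made, are where a reader would look for it.

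**Working it through.** The documents give no treatment-emergent or compliance figure to reproduce. The check is a comparison of passages plus day arithmetic from the visit schedules, with no Day 0.

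**1. STOP run-in as a share of the window**

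Inputs: Visit 1 is d = 10 to 30 days before Day 1; blinded treatment is 84 days; open observation is 84 more. Share = d / (d + last day of window).

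| Window ends | d = 10 | d = 30 |
|---|---|---|
| Day 84 | 10/94 = 10.6% | 30/114 = 26.3% |
| Day 168 | 10/178 = 5.6% | 30/198 = 15.2% |

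In a window to Day 168, open observation is a further 84/178 = 47.2% (d = 10) or 84/198 = 42.4% (d = 30). If a Day 0 is counted, the run-in is 11 to 31 days. The SAP's own STOP schedule lets Visit 2 fall up to 8 days late, which stretches the longest run-in to 38 days. Opening the window at the first study dose brings all of these to 0.

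**2. START columns**

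Inputs: 80 patients planned, equal split between blocks expected (Protocol 3.2), 1:1 allocation (Protocol 3.5.1). That gives 40 in START and 20 per arm. Assume all complete 56 days. Placebo patients spend 28 days on each treatment.

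| How switched patients are placed | Placebo column | HCQ column |
|---|---|---|
| By first treatment (randomised arm) | 20 patients, 20 × 56 = 1120 days | 20 patients, 1120 days |
| Under HCQ once any HCQ is taken | 0 patients | 40 patients, 40 × 56 = 2240 days |
| Split at the switch | 20 patients, 20 × 28 = 560 days | 40 patients, 1120 + 560 = 1680 days |

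Under the second reading, 560 of the 2240 days in the HCQ column (25%) were on placebo. SAP 2.1 does not choose among the three. Only the split keeps placebo time apart from HCQ time, and the comparison with placebo also needs the HCQ arm cut at Day 28.

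**3. Listings against tables**

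SAP 6 limits AE output to listings. SAP 6.7.2.1 asks for a subject listing and also for tables of numbers and percentages. Both cannot stand. With listings only there are no columns, and steps 1 and 2 lose most of their effect.

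**4. Compliance of a patient who takes every capsule**

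Assumption: one capsule a day. The formula implies this, but the documents do not state it. Score = 100 × dosing days / (lead days + days to study end).

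| Block and study end | Shortest lead | Longest lead |
|---|---|---|
| START, Day 56 | 7 days: 56/63 = 88.9% | 28 days: 56/84 = 66.7% |
| STOP, Day 84 | 10 days: 84/94 = 89.4% | 30 days: 84/114 = 73.7% |
| STOP, Day 168 | 10 days: 84/178 = 47.2% | 30 days: 84/198 = 42.4% |

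The START schedule allows Visit 1 as late as Day -3. Randomising then would break the 1-week footnote, and would still give only 56/59 = 94.9%. Counting from the first dose over the dosing days due gives 100%.

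**The case against.** **The early STOP opening looks deliberate.** The SAP schedules mark AEs at Visit 1 in STOP but not in START, and SAP 4.2.2 writes its exemption for START alone. STOP patients are already on HCQ, and safety after more than 3 months is an objective. This stands as a reason to keep and report run-in events. It does not make open-label HCQ study medication, and it does not justify showing those events under placebo.

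**The effect is conditional.** If the listings-only sentence governs, no placebo column exists. That is right. The SAP reports too few patients for the combined analysis of both blocks, so listings alone may have been intended. But 6.7.2.1 still sets out the tables in detail, and the SAP has to say which applies.

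**The open end of the STOP window.** A reader might infer that this is an error in itself, because Visit 5 carries the end-of-trial label and Protocol 7.3 stops AE collection at the end of trial. The documents do not support that. The rule has no upper limit and both schedules mark AEs to Day 168, so Day 168 is the natural reading. What remains is that one window pools blinded treatment with open observation.

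**A diluted rate ratio.** A reader might convert the run-in share into a shrunken HCQ-to-placebo AE rate ratio. The documents do not support such a figure. The planned tables count patients with at least one event, not rates over time. The half-lives in Protocol 1.3 (18 days for the slow phase, 30 to 60 days overall) also mean that STOP placebo patients stay partly exposed after Day 1.

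**Compliance is minor.** It is descriptive, the lead time arises in both arms alike, and SAP 2.3 drops the per-protocol analysis, so it feeds no analysis population. This stands. The 42% to 47% range also needs study end to be read as Day 168.

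**Conclusion.** The point holds, within limits. The STOP opening contradicts the SAP's own definition and brings in 10 to 30 pre-dose days: 10.6% to 26.3% of a window to Day 84, or 5.6% to 15.2% of one to Day 168. START patients who receive both treatments have no assigned column, so the comparison with placebo to Day 28 is not isolated. Both matter for reported results only if the tables in SAP 6.7.2.1 are produced, and the SAP contradicts itself on that.

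The compliance formula is a smaller fault. On the assumption of one capsule a day, full adherence scores 67% to 89% in START and 74% to 89% in STOP to Day 84, and lower if study end is Day 168.

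AE analysis is descriptive and the primary outcome is untouched. What is at stake is what the safety tables show and how they can be read. The size of any distortion in the percentages of patients with AEs cannot be derived from the documents. This should be corrected because safety is a stated objective in both blocks and the correction is cheap.

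**What to change.** 1. **SAP 6:** delete the listings-only sentence, or limit it to listings beyond the tables in 6.7.2.1.
2. **SAP 6.7.2.1, STOP:** open the treatment-emergent window at the first study dose (Visit 2). Tabulate Visit 1 to Visit 2 separately as run-in on open-label HCQ, which serves the objective on more than 3 months of treatment. State the window end, and tabulate Day 1 to 84 and Day 85 to 168 separately.
3. **SAP 6.7.2.1 and 2.1, START:** tabulate Visit 2 to Visit 3 by treatment received, as the placebo comparison. Tabulate events after the switch separately, as on HCQ, by randomised arm.
4. **Missing start dates:** place these AEs by the visit at which they were first recorded, and otherwise in the blinded window (STOP Day 1 to 84, START Visit 2 to Visit 3).
5. **SAP 6.5:** use 100 × capsules used / capsules due from the first study dose to the last planned dose or the date of permanent discontinuation. Report discontinuation separately, so that it is not mixed with adherence.

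The cost is SAP wording and a few more descriptive tables, some with small counts. No new AE data are needed: onset is defined in Protocol 7.1, the cuts use visit dates, and Protocol 4.1.7 already has capsules dispensed, used and returned recorded. Compliance also needs the number of capsules due per day for each patient.

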6.7.2.2 Laboratory Parameters

Listings will be prepared for each laboratory measure and will be structured to permit review of the data per subject as they progress on treatment.

Summary tables will be prepared to examine the changes of laboratory measures over time by descriptive statistics and exploratory p-values.

6.7.2.3 *Vital Signs*

Absolute values and changes from baseline of the vital signs will be analysed descriptively and by exploratory p-values.

6.7.2.4 *Others*

Not applicable.

6.7.3 *Quality of Life (Peds QL)*

Each item will be reversed scored and linearly transformed to a 0-100 scale as follows:

0=100, 1=75, 2=50, 3=25 and 4=0 (higher scores indicate better quality of life).

If more than 50% of the items in a scale are missing, the scale score should not be computed.

Mean scores are defined as sum of the items over the number of items answered.

The psychosocial health summary score is the sum of the items over the number of items answered in the emotional, social and school functioning scales.

The total score is the sum of all items over the number of items answered on all the scales.

Descriptive statistics and exploratory p-values (t-tests with unequal variances) for absolute values and changes to baseline will be tabulated.

6.7.4 *Health economics*

The analysis will not be done by the IZKS.

6.8 *Subgroup Analyses*

Not applicable.

6.9 *Interim Analysis*

No interim analysis is planned.

7 Software

All analyses will be performed using the Statistical Analysis Software (SAS), Version 9.4.

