## 1.2 Trial rationale

### The impact

So far, there exist no controlled studies to evaluate the efficacy of the different treatment options in chILD. In practice beside steroids hydroxychloroquine and macrolide antibiotics are often used drugs for the treatment of chILD (Clement 2010).

Due to the rareness of the diseases only international studies can collect sufficient numbers of patients. Therefore we will use the European wide project on chILD, the chILD-EU project, to implement a randomized controlled study to evaluate the pharmacological treatment of chILD.

This international study will address all these issues and will help to create new knowledge for everyday care in this broad group of pediatric interstitial lung diseases.

With this study we aim to

- Evaluate the efficacy of hydroxychloroquine against placebo in chILD
- Evaluate the safety of mid-term use of hydroxychloroquine
- Be able to make a decision on the risk and benefit of the use of hydroxychloroquine
- Help standardizing the pharmacological treatment of chILD

Currently HCQ is used off-label in a wide range of clinical severity, ranging from respiratory insufficiency to minimal respiratory symptoms. So far it is not predictable which patients will respond to the treatment and which will not. Due to this fact and due to the rareness of the diseases the goal of this exploratory study is to include patients with different symptoms and a wide range of clinical severity to sample as much information about this topic as possible to improve the treatment of this group of patients. Therefore, the character of this study is explorative and not confirmative.

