## 1.4 Summarized risk-benefit assessment

### The need for a trial:

So far for children with chILD no randomized or controlled trials have been performed. As almost each individual symptomatic child is empirically treated with the entire spectrum of potential drugs, we urgently need to clarify which patients, and if any at all, might benefit from this treatment and which will not. This is necessary to improve the everyday care, and to direct treatment of the patients with the chILD. Such knowledge will also reduce treatment burden in children who are treated despite the fact that this might not be effective.

As the type of diseases investigated in this trial, as well as the course of the diseases and the effects of the drug are not sufficiently similar in adults and pediatric patients, pediatric effectiveness

cannot be extrapolated from studies in adults. Almost all disease in question are unique to infants and children. Thus studies in adults cannot (and do not) exist, as type and course of diseases is specific for children. Thus the studies must be done in the population primarily affected by the diseases (chILD). In other settings no relevant results can be expected.

The clinical research interventions and procedures planned represent an appropriate balance of risk and potential benefit. Specific protections were implemented to ensure adequate protection for minors, including parental permission and assent of able children, assurance of direct benefit for the child or for the group of patients with the particular condition, and minimization of risk. The risks to which the children are exposed are low, both compared to the potential therapeutic benefit and the risk of the disease. Due to the cross-over design of the START trial, the children are neither placed at a disadvantage by being enrolled, nor failing to get necessary health care.

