#### 3.2 Number of subjects

It is planned to assess >100 subjects for eligibility and to allocate 80 subjects. Recruitment and treatment of subjects is expected to be performed in up to 100 trial centres. We expect an equal distribution between START and STOP blocks.

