1.2 Study Design

[figure not shown]
[figure not shown]
This study is an explorative, prospective, randomized, double-blind, placebo controlled investigation of hydroxychloroquine (HCQ) in pediatric ILD. The treatments are organized in START and STOP blocks, which can be initiated in sequence, as needed by the subjects. Each patient can participate in each block, but only once in each block.

In the START block subjects are randomized to parallel-groups, then the placebo group is switched to active drug.

In the STOP block, subjects on HCQ are randomized into parallel-groups treated with placebo or HCQ to investigate the withdrawal of HCQ for assessment of its efficacy.

It is planned to assess >100 subjects for eligibility and to allocate 80 subjects. An equal distribution between START and STOP blocks is expected.

Study flow chart

Trial schedule START HCQ Block

Visit	Screening evaluations and Visit 1	Visit 2	No Visit	Visit 3	No Visit	Visit 4
Action	„Start of baseline“	“End of baseline“ + Day 1 of treatment	Every 7 days at home + web/tele feed-back	End of 1 st Tx period	Every 7 days at home + web/tele feed-back	“End of trial“
Trial day	-28 to -3	1		28 (-4, +7)		56 (-4, +7)
Demographics (e.g. sex, age, race)	X					
Patient information, informed consent	X					
Previous and concomitant diseases	X	X		X		X
Previous and concomitant treatments	X	X		X		X
Inclusion/exclusion criteria	X					
Pregnancy test ^k	X			X		X
Randomization ^l	X					
Physical examination	X	X		X		X
Vital signs (BP, pulse, temp, cardiotoxicity, hypoglycaemia)	X	X		X		X
ECG	X*			X		X
Ophthalmologic review ^m	X*					
Lab ⁿ (GOT/GPT/Crea/BUN/CK/GGT/LDH/BB/DIFF drug level /save EDTA, blood glucose)	X*			X		X
pO ₂ , pCO ₂ (capillary)	X	X***		X***		X***
Primary outcome ^e O ₂ -sat. in room air	X	X	-	X	-	X
Secondary outcomes						
Respiratory rate, in room air	X	X	X	X	X	X
Retractions	X	X	X	X	X	X
Coughing	X	X	X	X	X	X
Oxygen demand	X	X	X	X	X	X
Chest x-ray scoring for child	X*			X****		
Pulmonary hypertension (Echo)	X*					
Quality-of-life ⁱ	X*					X
Health Economics ^h	X*					X
Weight for height ^b	X*					X
Adverse events		X	X	X	X	X
Additionally in children > 5 years						
FEV1 % predicted (recorded in L) ^d	X	X		X		X
FVC % predicted (recorded in L) ^d	X	X		X		X
6 minute walking distance (meter) ^g	X	X		X		X
O ₂ -saturation before and after 6MWT	X	X		X		X
Borg scale ^j	X	X		X		X
Additionally in ventilated patients						
Oxygenation index (OI)	X	X	X	X	X	X

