6.6 Primary Analysis

The variable assessing the primary outcome is the response rate measured by the oxygen saturation in room air.

START HCQ block

Relative change from trial day 1 (Visit 2) to day 28 (Visit 3) and day 56 (Visit 4) and from day 28 to day 56 change from active compound compared to change from placebo

STOP HCQ block

Relative change from trial day 1, i.e. Visit 2, through day 84, i.e. Visit 5: change from active compound compared to change from placebo

Both blocks separately

a) A difference between the changes in placebo and active phases is considered significant as described in the table below.

Patient's condition	Measured parameter	Definition of significant change or responder
Stable in room air or on	SpO2 in room air	Increase $\geq 5\%$

O2-supplement		
On high-flow nasal cannula	O2-flow, air-flow	Decrease $\geq 20\%$ or support not needed any more
Ventilated	Oxygenation index	Decrease $\geq 20\%$ or support not needed any more
On ECMO		Decrease $\geq 20\%$ or support not needed any more

The analysis will be done first by discarding the information on the patient's condition. Descriptive analyses will be done overall and for all patients conditions separately.

b) Patients are defined as responder as described in the table above. The numbers of responders are counted and compared by Fisher's exact test as well as logistic regression models with factors for treatment group and age group.

The following SAS code can be used:

```
PROC LOGISTIC DATA=indata;
  CLASS treatment age_gr;
  MODEL responder_YN = treatment age_group treatment*age_group;
RUN;
```

Both blocks together

Not applicable. There were too few patients in both blocks.

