6.7 Secondary Analyses

All analysis of secondary endpoint will be interpreted purely exploratory. For all hypotheses two-sided exploratory p-values will be provided. Descriptive statistics will be displayed for all.

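### No between-arm estimate with a confidence interval is planned for laboratory values, vital signs, adverse events or responders, and at about 20 patients per arm a p-value alone says little about safety or effect

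*SAP*

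**What the plan says.** Laboratory values (SAP 6.7.2.2): "Summary tables will be prepared to examine the changes of laboratory measures over time by descriptive statistics and exploratory p-values". The text does not say whether these p-values compare arms or visits, and it names no test.

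Vital signs (SAP 6.7.2.3): "Absolute values and changes from baseline of the vital signs will be analysed descriptively and by exploratory p-values".

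Adverse events (SAP 6.7.2.1): numbers and percentages of patients, with no p-value and no interval. A line in SAP section 6 says adverse-event data will appear only as listings, which does not fit the tables planned in 6.7.2.1.

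Responders (SAP 6.6 b): "The numbers of responders are counted and compared by Fisher's exact test". A logistic regression is added. The text gives it factors for treatment and age group, and the sample code also includes their interaction. No odds ratio, risk difference or interval is requested.

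Secondary analyses in general (SAP 6.7): "For all hypotheses two-sided exploratory p-values will be provided".

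The default summaries in SAP section 6 cover number, mean, SD, median, quartiles and range, by treatment group and in total. They contain no interval. The one interval named in the SAP is for median overall survival (6.7.1).

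Safety is a secondary objective in both blocks (Protocol 2.2, SAP 1.1). Protocol 1.2 lists among the trial's aims: "Be able to make a decision on the risk and benefit of the use of hydroxychloroquine".

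**The concern.** A risk-benefit decision needs to know how large a harm, or how large a benefit, the data still allow. A confidence interval answers that and a p-value does not. In a small trial most comparisons can be expected to be non-significant, whether or not HCQ does anything. Protocol 1.4 also hopes to spare children a treatment that may not work: "Such knowledge will also reduce treatment burden in children who are treated despite the fact that this might not be effective". A conclusion of that kind would rest on null results, and for a null result the width of the interval is the main information.

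At stake is what the report can say on its safety objectives and on a null responder comparison. Without a pre-specified interval, the only planned inferential result for laboratory values and vital signs is a p-value from an underpowered test.

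**Working it through.** **Inputs from the documents**
- Total: "It is planned to assess >100 subjects for eligibility and to allocate 80 subjects" (Protocol 3.2).
- Split: "An equal distribution between START and STOP blocks is expected" (SAP 1.2). Allocation within each block is 1:1 (Protocol 3.5.1).
- Patients per arm: 80 / 2 blocks / 2 arms = 20.
- Withdrawn patients are not replaced (Protocol 3.6.3) and missing values are not filled in (SAP 5.1), so the analysed number can be lower.
- Protocol 8.1 gives no calculation behind the 80, so there is no planned power figure to reproduce.

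**Assumptions.** Tests are two-sided in the documents, but no level is stated; 5% is assumed. The between-arm t-test, effect sizes, event rates and example counts are illustrations.

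**1. Continuous safety measure, two-sample t-test, n = 20 per arm**
- Noncentrality = d × √(n/2). For d = 0.5 SD this is 0.5 × √10 = 1.58, with 38 degrees of freedom.
- Power = 0.338, so the difference is missed 66% of the time. The normal approximation gives power 0.352, missed 65%.
- A 0.8-SD difference is missed 31% of the time. Power of 80% needs a true difference of 0.91 SD.
- With 15 analysed per arm, power for 0.5 SD is 0.262, missed 74%.
- By the normal formula, 80% power for 0.5 SD needs 2 × (1.960 + 0.842)² / 0.5² = 62.8, that is 63 per arm.

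**2. What an interval would show for the same measure**
- 95% half-width = t(0.975; 38) × √(2/20) = 2.024 × 0.316 = 0.64 SD.
- An observed difference of exactly zero would leave -0.64 to +0.64 SD open, so a 0.5-SD harm would not be excluded. The interval makes this visible.

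**3. Binary outcome, Fisher's test, n = 20 per arm**
- Power by full enumeration: 24% for 10% against 30%; 49% for 10% against 40%; 41% for 20% against 50%.
- Example 6/20 against 2/20: Fisher p = 0.24. The Wilson limits are 0.146 to 0.519 and 0.028 to 0.301. The Newcombe interval for the difference of 0.20 is:
  - lower: 0.20 - √[(0.300 - 0.146)² + (0.301 - 0.100)²] = -0.05
  - upper: 0.20 + √[(0.519 - 0.300)² + (0.100 - 0.028)²] = +0.43

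**4. No event observed**
- One-sided 95% upper bound = 1 - 0.05^(1/n): 13.9% for 0/20 and 7.2% for 0/40.
- Upper limit of the two-sided exact 95% interval = 1 - 0.025^(1/n): 16.8% and 8.8%.

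**The case against.** The trial is openly exploratory. The protocol says so in 1.2, gives no sample size calculation in 8.1, and labels its p-values and secondary analyses exploratory throughout. Low power at this size is no surprise, and intervals would change no estimate, test or dataset.

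Three stronger readings are tempting, and the documents do not support them.

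- *That a non-significant result will be taken as proof of safety or of no effect.* No section states such a rule. The risk-benefit aim in Protocol 1.2 and the motivation in 1.4 are not tied to any test.
- *That readers would have nothing but p-values.* By-arm number, mean and SD are default output, responder counts are given by arm, laboratory data are listed per patient, and Protocol 8.5 adds shift tables. A reader could derive most intervals from these. Adverse events carry no p-value at all, and the SAP specifies none for on-treatment ECG or eye findings, so the p-value criticism is limited to laboratory values, vital signs and responders.
- *That a null Fisher test in STOP would show withdrawal to be harmless.* The responder table in SAP 6.6 defines only improvement, for both blocks. The deterioration definition for withdrawal is in the protocol's responder table (8.3.1). As the SAP stands, the STOP test compares improvement rates and does not address harm from withdrawal.

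Nor does 0.5 SD describe the Fisher comparison, which has no SD scale, and no section calls 0.5 SD a relevant harm.

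These objections limit the size of the point but do not remove it. An exploratory trial is there to estimate, and an interval is the natural output of estimation. Leaving readers to construct intervals is weaker than committing to them. The logistic model does not fill the gap, because no estimate is requested and, with the interaction in the code, its treatment term is not one overall effect.

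**Conclusion.** The point holds as a minor-to-moderate reporting improvement. The SAP pre-specifies no between-arm estimate with a confidence interval for laboratory values, vital signs, adverse-event proportions or the responder comparison, although safety is a secondary objective in both blocks and a risk-benefit decision is an aim. At the planned 20 or so per arm, a 0.5-SD difference in a continuous safety measure would be missed about two times in three. An observed 20-point difference in proportions can be non-significant with limits from -5 to +43 points, and no events in 20 patients still allows a rate of about 14%.

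The absence of intervals is plain from the text. The magnitudes rest on full, equal recruitment with no loss, a two-sided 5% level, a between-arm test for laboratory values, and illustrative effect sizes and counts. Fewer analysed patients would make the miss rates higher and the intervals wider.

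**What to change.** - **SAP 6.7.2.2 and 6.7.2.3:** report the between-arm difference in change with its 95% interval, in place of or beside the exploratory p-value. Use Day 28 in START, before placebo patients switch to HCQ, and Day 84 in STOP. State that the comparison is between arms. An unequal-variance interval would match the t-test already named in SAP 6.2 and 6.7.3. For laboratory values the baseline is the screening sample, because none is scheduled at Visit 2.
- **SAP 6.7.2.1:** add exact 95% intervals by arm for the percentage of patients with any adverse event, any serious event and any related event. Include the upper bound when no event is seen, and say whether that bound is one- or two-sided. Reconcile this section with the listings-only line in section 6.
- **SAP 6.6 b):** beside the Fisher p-value, give the difference in responder proportions with a Newcombe or exact 95% interval.
- **STOP block:** reconcile the SAP responder table with the protocol's definition for withdrawal. The interval can inform on harm from withdrawal only if deterioration is what is counted.
- **SAP section 6:** state that a non-significant p-value will not be taken as evidence of safety or of lack of effect, and that such statements will refer to the confidence limits.

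The cost is SAP wording and a few lines of output, with no new data and no extra patients. The drawback is that the intervals will be visibly wide, so the report's safety and null-efficacy statements will have to be more guarded.
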